1.2 Description of the drug under study

Panhematin[™] is a sterile, lyophilized powder suitable for intravenous administration after reconstitution. Each dispensing vial of Panhematin[™] contains the equivalent of 350 mg hemin, 240 mg sodium carbonate and 355 mg of sorbitol. The pH may have been adjusted with hydrochloric acid; the product contains no preservatives.

When mixed as directed with sterile water for injection, USP, each 48 mL provides the equivalent of approximately 336 mg hematin (7 mg/mL). When reconstituted with 147 mL of 25% human serum albumin instead of sterile water, which is an off-label recommendation, the hemin concentration is 2.4 mg/mL. ⁵⁰

In this study Panhematin[™] will be reconstituted with 25% human albumin, which has been found to enhance stability and reduce side effects such as infusion site phlebitis and transient coagulopathy ^{43,50,51}. Phlebitis and coagulopathy after reconstitution with sterile water result from degradation products that bind to vascular endothelial cells, platelets and circulating coagulation factors.

1.3 Rationale for this clinical trial

The quality of the evidence base for diagnosis and treatment is becoming increasingly important in clinical practice, even for uncommon disorders. Hemin treatment can be rated no higher than 1C based on current evidence-based evaluation ⁶⁵. The lack of strong evidence for efficacy makes it more difficult to convince practicing physicians that patients will benefit, and therefore limits availability of this treatment for patients with acute porphyrias. Experience has shown that some physicians regard this treatment as still "experimental."

The low quality of the evidence applies to use of hemin for treatment of acute attacks of porphyria and also to its use for prevention of such attacks. A separate double blind placebo controlled study protocol aims to improve the quality of the evidence for use on Panhematin[™] for treating acute attacks. This protocol addresses its use for prevention of frequently recurring attacks of porphyria. This study is important because there is evidence that Panhematin[™] is used quite frequently to prevent recurrent attacks of porphyria in the U.S.⁶⁴ and there have been few studies to guide or justify its use for this indication ^{9,66}. Product labeling supports its use for prevention of recurrent attacks in women. This is based on a single case report ⁶⁶, and it is generally believed that frequently recurring cyclic attacks are best treated with a hormonal intervention such as a GnRH analogue ⁶⁷. Therefore, the most promising and appropriate preventive use for hemin would likely be for frequently recurring noncyclic attacks.

This study, as well as the study in acute attacks, will not provide definitive evidence to support the changes in product labeling for Panhematin[™] in the U.S., but will contribute significantly to the body of evidence to support current expert recommendations in the following areas. 1) Current expert opinion is that at least for acute attacks, hemin treatment should be started promptly, without an initial trial of glucose ⁹. Product labeling recommends treatment with Panhematin[™] only after a trial of glucose for several days is not successful. Glucose loading is sometimes effective for treating mild acute attacks ⁹, but is seldom effective for preventing recurrent attacks, and often leads to unwanted weight gain. This study will likely provide evidence to support initial treatment with Panhematin[™] for prevention of frequently occurring attacks. 2) Although Panhematin[™] labeling states that treatment is approved only for treatment of women with attacks of AIP related to the menstrual cycle, there is no evidence from previous cases series

Porphyria Laboratory and Center Date: June 18, 2019 IND 13,929

that treatment response to hemin is different in men, in women when the attack is not related to the cycle or in HCP and VP. Therefore, this study will support the use of hemin for prevention of recurrent attacks of AIP, HCP or VP in men and in women with frequently recurring attacks unrelated to the menstrual cycle. 3) The study will provide evidence to support use of Panhematin[™] reconstituted with 25% human albumin to enhance stability and reduce side effects ⁵⁰ by demonstrating a low incidence of infusion site adverse effects. This method has become widely used in clinical practice, but published data supporting its use is limited. 4) The study will also focus on a dose of 4 mg/kg rather than the 1-4 mg/kg daily recommended in product labeling.

2. Objectives

Patients available for this trial will already be on a prophylactic hemin regimen, and as part of the study will be offered the usual number of periodic prophylactic hemin (or placebo) infusions, which for most patients will be a single weekly infusion. Patients will be offered blinded infusions that correspond to the number of infusions they usually receive within approximately one week for prophylactic treatment.

Primary Objectives:

- To evaluate in 20 patients who are on a Panhematin[™] prophylactic regimen whether a blinded dose of Panhematin[™] is more effective than placebo in preventing an attack within the next 1-4 weeks.
- To evaluate in these 20 patients whether hemin is as safe and well tolerated as placebo when administered in a blinded fashion. Safety parameters will include the frequency and severity of phlebitis, nausea, vomiting and coagulation abnormalities.

Secondary Objectives:

• To evaluate the biochemical effects of Panhematin[™] in patients treated with Panhematin[™] to prevent attacks of acute porphyria by measuring urinary 5-aminolevulinic acid and porphobilinogen and serum porphobilinogen. This will determine whether biochemical measurements are predictive of efficacy in preventing an attack.

Exploratory Objectives:

- To evaluate effects of clinical features, such as sex, age and the factors that precipitate attacks of porphyria on response to preventive administration of Panhematin[™].
- To evaluate effects of genetic features, including the nature or the *PBGD*, *CPOX* or *PPOX* mutation on response to preventive Panhematin[™]
- To evaluate the use of Panhematin™ reconstituted with 25% human albumin in patients treated to prevent acute attacks of porphyria

Porphyria Laboratory and Center Date: June 18, 2019 IND 13,929

2.1 Endpoints.

The primary efficacy endpoint is whether a Panhematin[™] is more successful than placebo in preventing a porphyria attack within the next 1-4 weeks when given as the patient's usual periodic prophylactic regimen given within approximately one week. Symptoms during past acute attacks should have included severe abdominal pain requiring a narcotic analgesic. An acute porphyric attack is defined by the presence of abdominal pain and one or more other characteristic manifestations such as tachycardia (heart rate 100 per minute or greater), nausea, vomiting, constipation, extremity pain, acute hypertension, low-grade fever, objective evidence of peripheral neuropathy, ileus, dehydration, mild leukocytosis, or hyponatremia. The manifestations of the recurrent attacks should have been similar to each other in nature (although not necessarily in degree or severity). The presence or absence of all such symptoms will be recorded on the CRFs by study personnel who are blinded to the treatment that was given.

The primary safety parameters will include the frequency and severity of phlebitis, nausea, vomiting and coagulation abnormalities. An additional series of safety measures will include other symptoms, physical findings and laboratory measurements.

Secondary efficacy endpoints will include urinary 5-aminolevulinic acid and porphobilinogen and serum porphobilinogen and comparisons of changes in these levels with prophylactic treatment with hemin and placebo.

Exploratory objectives. We will explore the effects of clinical features, such as sex, age, the factors that precipitate attacks of porphyria, and the nature of the *PBGD*, *CPOX* or *PPOX* mutation on response to Panhematin[™] prophylaxis. We will also gain experience on the use of Panhematin[™] reconstituted with 25% human albumin in patients treated to prevent acute attacks of porphyria.

3. Trial Design

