6.2.1.1 Number of attacks and porphyria-related signs and symptoms

At the post-treatment visits the patients will be queried about symptoms attributable to porphyria, treatment that was given for such symptoms and any doctor for hospital visits or admissions since the previous visit. Symptoms recorded will include pain, nausea, vomiting, constipation and specified neurological and psychiatric symptoms. This information will be recorded on the CRFs.

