6.3 Safety Assessment

6.3.1 Symptoms

Any new symptoms not related to porphyria will be recorded during the treatment period.

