6.3.6 Adverse Events

Adverse Events will be recorded at each visit.

7. Adverse Events

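### Nausea and vomiting serve both as primary safety parameters and as qualifying attack symptoms, so counting every episode biases that comparison toward hemin, while the attribution limit in 6.3.1 can dilute it

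*Combined protocol and SAP*

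**What the plan says.** The second primary objective (section 2) is "To evaluate in these 20 patients whether hemin is as safe and well tolerated as placebo when administered in a blinded fashion". Section 2.1 names the measures: "The primary safety parameters will include the frequency and severity of phlebitis, nausea, vomiting and coagulation abnormalities".

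Section 2.1 also defines the efficacy event: "An acute porphyric attack is defined by the presence of abdominal pain and one or more other characteristic manifestations such as tachycardia". The list of those other manifestations continues with "nausea, vomiting, constipation, extremity pain, acute hypertension" and further items. Section 6.2.1.1, under efficacy, collects the same complaints at post-treatment visits: "Symptoms recorded will include pain, nausea, vomiting, constipation and specified neurological and psychiatric symptoms".

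The safety sections do not agree on which episodes count:

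- Section 6.3.1 sets a limit: "Any new symptoms not related to porphyria will be recorded during the treatment period". It gives no criteria for relatedness and does not define the treatment period.
- Section 6.3.6 sets none: "Adverse Events will be recorded at each visit". The adverse event definition in section 7.1 requires no causal link and does not exclude attack symptoms.
- Section 12.2.2 lists symptoms as a safety endpoint without limit and plans between-group significance testing. Section 12.3 makes the adverse event analysis descriptive.

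**The concern.** One complaint feeds both primary objectives, and no rule says which episodes belong to the safety comparison. The text allows two readings.

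- **All episodes counted** (sections 2, 2.1, 6.3.6, 7.1, 12.2.2). Placebo patients who have attacks bring attack-related nausea and vomiting into the safety count. Each attack that hemin prevents removes some from the hemin arm. The tolerability result then partly restates efficacy.
- **Only episodes judged unrelated to porphyria** (section 6.3.1). Every participant has porphyria, and nausea and vomiting are listed porphyria symptoms. Drug-caused episodes can therefore be put down to the disease and never enter the symptom record. That draws the arms together, which favours a finding that hemin is as well tolerated as placebo.

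At stake is whether two of the four primary safety parameters can answer the question set for them. There is also a smaller blurring effect. Attacks may be treated with open-label Panhematin (sections 3.1, 4.5, 5.6), so without a time limit, nausea caused by hemin given later to placebo patients could enter the placebo count.

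**Working it through.** **Inputs from the plan.** Section 12.4 gives example attack probabilities of 0.8 (control) and 0.2 (treatment), and a second scenario of 0.8 and 0.38. It gives no figure for nausea or vomiting. As a check that the probabilities are read as the plan uses them: an uncorrected two-sided 5% comparison of proportions with 10 per group gives 81.7% power at 0.8 versus 0.2 (the plan says 80%). At 0.8 versus 0.38 it needs 21 per group, with 79.4% power at 20 per group (the plan says 20 per group).

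**Assumed inputs.** The documents give neither of these:

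- s, the share of attacks that include nausea or vomiting
- h, the probability that hemin itself causes it

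The pair 0.4 versus 0.2 is likewise an assumed scenario with a smaller attack difference. Other causes are taken as equal in both arms and left out; attack-related and drug-caused episodes are taken as independent.

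**Reading 1, all episodes counted.** With attack probabilities pc (placebo) and pt (hemin):

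- Placebo rate = pc × s
- Hemin rate = 1 − (1 − pt × s)(1 − h)

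Worked case: pc = 0.8, pt = 0.2, s = 0.5, h = 0.20. Placebo = 0.8 × 0.5 = 0.40. Hemin = 1 − (0.90 × 0.80) = 0.28. A true drug effect of +20 points appears as −12.

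Results at h = 0.20:

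| pc | pt | s | Placebo | Hemin | Hemin minus placebo |
|---|---|---|---|---|---|
| 0.8 | 0.2 | 0.25 | 20% | 24% | +4 points |
| 0.8 | 0.2 | 0.5 | 40% | 28% | −12 |
| 0.8 | 0.2 | 0.7 | 56% | 31% | −25 |
| 0.8 | 0.2 | 0.9 | 72% | 34% | −38 |
| 0.8 | 0.38 | 0.5 | 40% | 35% | −5 |
| 0.4 | 0.2 | 0.5 | 20% | 28% | +8 |

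**Where the sign changes.** At 0.8 versus 0.2 and h = 0.20, setting 0.8s = 0.2 + 0.16s gives s = 0.2/0.64 = 0.31. Below that share hemin looks worse than placebo. For fixed s, the break-even drug effect is h = 1 − (1 − pc × s)/(1 − pt × s). At s = 0.5:

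- 0.8 versus 0.2: 1 − 0.60/0.90 = 0.33
- 0.8 versus 0.38: 1 − 0.60/0.81 = 0.26
- 0.4 versus 0.2: 1 − 0.80/0.90 = 0.11

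A drug effect above these values would still show as harm, but understated.

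**Chance that a trial of this size shows the reversal.** With 10 per group, 0.8 versus 0.2 and h = 0.20, the observed hemin count falls below the placebo count with probability 31% at s = 0.25, 63% at s = 0.5 and 89% at s = 0.8.

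**Reading 2, section 6.3.1 governs.** If attack symptoms are correctly set aside, the placebo rate in this model is 0 and the hemin rate is h, so the masking goes. But if a fraction a of drug-caused episodes is judged porphyria-related, the recorded difference is h × (1 − a). The documents give nothing from which a could be set, and no criteria that would limit it.

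**The case against.** The strongest reply is that section 6.3.1 already separates the two: attack symptoms go to efficacy under 6.2.1.1 and the rest to safety, so the bias toward hemin never arises. Symptoms are also recorded by blinded staff, so misattribution should not favour one arm, and adverse events are collected whatever their cause. If the treatment period means the treatment visit, which lasts from one day to about a week (section 3.1), most attacks in the 4-week follow-up fall outside the symptom record.

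Much of this stands. Nothing in the documents says that attack-related nausea will be counted for safety. Blinding does prevent attribution from systematically favouring an arm, but it does not stop true drug-caused episodes from being removed, and that dilutes the difference. Adverse event recording softens this without settling whether attack symptoms are included. A short treatment period would shrink the masking, but the term is undefined and sections 2.1 and 12.2.2 do not repeat the limit.

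It is also fair that h has no source. The side effects of hemin and albumin listed in sections 1.1 and 13.1 do not include nausea or vomiting, and the attack rates are only an example. The overlap can work against hemin too: drug-caused nausea in a patient with abdominal pain could qualify as an attack. And the trial is small: 6 of 10 versus 3 of 10 gives a Fisher p-value of 0.37, so a formal test would rarely decide the matter.

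**Conclusion.** The concern holds in conditional form. Counting every episode biases the nausea and vomiting comparison toward hemin to the extent that hemin prevents attacks, and can hide or reverse a drug effect. Under section 6.3.1 the risk is dilution by attribution instead. The plan does not say which rule applies.

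The size rests on assumed s and h. At the plan's example rates with h = 0.20, the observed rates are 40% versus 28% (s = 0.5) to 72% versus 34% (s = 0.9), placebo versus hemin.

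A reader might infer more than the documents support:

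- That hemin is bound to look safer than placebo. It is not: the sign depends on the attack difference, s and h.
- That hemin is known to cause nausea. The documents do not say so.
- That the whole safety objective is compromised. Phlebitis and coagulation abnormalities are not part of the attack definition and are unaffected.
- That nausea or vomiting is needed for an attack. Abdominal pain is the required element; these are two of many optional second elements.

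This is an inexpensive improvement to a stated recording rule that serves a primary objective. It does not call for any change to treatment or sample size.

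**What to change.** 1. **Section 6.3.1:** record all new symptoms with onset time, whatever the attributed cause.
2. **Sections 2.1 and 12.2.2:** make the main nausea and vomiting safety comparison all episodes that start during, or within a prespecified short window (for example 24 h) after, each blinded study infusion and before any open-label Panhematin, regardless of attribution. The length is the sponsor's choice; the documents supply no basis for a particular value. State that the blinded attack-treatment dose described in sections 5.3 and 5.6, which reverses the assigned treatment, also closes the window and does not open a new one.
3. **Tables:** show episodes inside and outside recorded attacks separately, together with the all-episode count over follow-up.

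The main comparison should not be restricted to episodes outside attacks. That would condition on an outcome that treatment is meant to change, and would still depend on judging when an attack began. A short window leaves some pull toward hemin from attacks that begin inside it, but far less than a 4-week count, and the separate tabulation makes it visible.

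The cost is one CRF field and one extra table. The downside is that late drug effects appear only in the secondary table.

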3.1 Type of Trial

The trial is a double-blind, randomized, placebo-controlled, parallel group trial investigating the efficacy and safety of Panhematin[™] for preventing acute attacks in at least 20 patients with well-documented acute porphyria (AIP, HCP or VP). These patients will (1.) have had frequent attacks in the past, with symptoms such as abdominal, back and/or limb pain and diagnosed after exclusion of other causes, and (2.) be on hemin prophylaxis for prevention of frequent attacks. Although clear guidelines have not been developed, it is expected that patients will have had 6 or more attacks in one year before starting hemin prophylaxis. This would be considered justification for a preventive regimen of hemin on clinical grounds. Most patients on hemin prophylaxis are given a single dose once weekly. However, other prophylactic regimens are effective in some patients, such as twice weekly infusions or a series of 3-4 infusions at monthly intervals. Giving only one blinded infusion may not be meaningful for a patient for whom more than a single infusion is needed to prevent attacks. Therefore, patients will

be offered the number of blinded infusions they usually are given within approximately one week for prophylaxis. All infusions for each patient will be either Panhematin[™] or placebo. An interim analysis will be carried out after completion of ~10 patients to assess progress and possibly adjust the sample size. The trial consists of the following:

- A screening visit to determine eligibility and obtain informed consent
- A treatment visit for administration of one or more double blind prophylactic doses of Panhematin[™] or placebo, corresponding to each patient's usual prophylactic regimen. Depending on the regimen, this visit may be completed in one day or after the number of days corresponding to their usual prophylactic regimen over approximately one week.
- Follow up visit at 1, 2, 3, and 4 weeks to assess response to the infusion of Panhematin[™] or placebo. These visits will be in person or by telephone.
- Additional visits may be scheduled if needed, for example for treatment of symptoms.
- Follow-up visits 3 and 6 months after the end of treatment either in person or by telephone

Patients will have laboratory documentation of one of the acute porphyrias. Molecular documentation is also expected, although rarely a causative mutation cannot be detected. Upon entry into the study they will be given in a blinded fashion one or more preventive dose of either PanhematinTM (4 mg/kg) or placebo. The number of infusions will correspond to the number of prophylactic doses of hemin they customarily receive over approximately one week. A recurrent attack within the next 1, 2, 3 and 4 weeks will represent treatment failures. Because at study entry most patients are expected to be on weekly prophylactic hemin treatment, and hemin is a short-acting drug, emphasis in the analysis will be on attacks occurring within 1 week after study treatment.

Any attacks that occur during the study will be treated according to standard of care, which may include Panhematin[™], either at the study site or at the patient's usual treatment location.

It is intended that 20 patients will complete treatment with a single blinded dose and at least 4 weeks of follow up. A completed patient is one who meets all entrance criteria, has no exclusion criteria and completes the single dosing and at least one week of follow up, or is withdrawn because of an adverse event.

The site for this study is the University of Texas Medical Branch (UTMB) at Galveston. The UTMB Porphyria Laboratory will carry out laboratory determinations related to porphyria as needed for this study. DNA studies to identify the familial mutation are now standard of care and will not be done as part of the study.

Porphyria Laboratory and Center Date: June 18, 2019 IND 13,929

3.2 Rationale for the trial design

A randomized, double-blind, placebo controlled study design is important for evaluation of clinical efficacy of a treatment or preventive regimen for acute porphyrias because the symptoms of these disorders (e.g. pain) are highly variable and subjective. Physical signs other than pulse and blood pressure are also at least somewhat subjective. A single dose of blinded treatment, or the number of doses corresponding to patients' usual prophylactic treatment over approximately one week, was adopted because a blinded study of an extended course of preventive treatment would require repeated treatment visits to the study site, which is difficult unless a patient lives close to the site. Also, most patients on hemin prophylaxis have been on a preventive regimen for an extended period, and are not available to be studied when prophylactic Panhematin[™] is initiated. On the other hand, many more patients are available who can travel even long distances to UTMB for a study that focusses on prophylactic dosing for less than approximately one week.

A single dose or multiple doses of study drug within approximately one week does not fully test the effectiveness of a continued regimen of hemin prophylaxis. However, if Panhematin[™] prophylaxis is effective in preventing attacks, a difference should be seen between the Panhematin[™] and placebo groups in the effectiveness in preventing an attack over the next 4 weeks. However, some patients may not remain constantly susceptible to attacks, and at times might not have an attack after a single dose of placebo. Therefore, efficacy data will be collected for 4 weeks or until the next time the patient is treated with Panhematin[™] (either for an acute attack or for prophylaxis), whichever is longer. Given the uncertainty of the follow up interval that will be most informative, and other related uncertainties, an interim analysis will be done after the first ~10 patients to see if an adjustment in sample size or other protocol modification may be needed.

Both groups will receive either a single dose, which can presently be considered the standard dose of Panhematin[™] for a prophylactic regimen, or the individualized prophylactic regimen that has been judged clinically to be effective in an individual patient when given during approximately one week. Any recurrent acute attacks that occur during the study will be treated as part of the study (i.e. with glucose or Panhematin[™]). Observations made during treatment of individual patients will be made available to their doctors at the end of the study and may contribute to their future management.

Potential study participants will be identified through the Porphyrias Consortium and its Longitudinal Study or referred by the American Porphyria Foundation as well as physicians countrywide.

